This project will fill several knowledge gaps by characterizing the underlying mechanisms and metabolic signatures of stress hyperglycemia with the use of comprehensive metabolic profiling methods and provide proof-of principle with the use of novel therapies for the prevention and management of stress-hyperglycemia.

Aim 1. To examine baseline and postoperative metabolic profiles of non-diabetic CABG patients with stress hyperglycemia. With a case-control design we will conduct the following analyses:

1.1 Targeted Approach: To determine cross-sectional and longitudinal changes of BCAA, ceramides, acylcarnitines, inflammatory markers, and a biomarker panel for CV risk [CRP + FDP + HSP-70, SuPAR] and their relationship with stress hyperglycemia (BG >140mg/dl) and insulin resistance estimates. *We hypothesize that elevated ceramides, acylcarnitines, branched-chain amino acids (BCAAs) are associated with incident stress hyperglycemia, and that hyperglycemia leads to changes in path-specific biomarkers related to CV risk.*

1.2 Untargeted Analysis: Utilizing untargeted HRM analyses, we aim to identify additional candidate metabolites and metabolic pathways associated with incident stress hyperglycemia during cardiac surgery. *We hypothesize that known (candidate metabolites) and previously unrecognized metabolites and pathways are associated with hyperglycemia during surgical stress.*

1.3 Integrative analysis: Metabolome-wide association studies (xMWAS) and integrative network analyses will be conducted to find multilevel associations between metabolites, biomarkers, and stress-hyperglycemia. *We hypothesize that multiple factors associated with diabetes and cardiovascular disease are interrelated and predict hyperglycemia during stress conditions.*

Aim 2. To obtain preliminary estimates of the effect of a long-acting GLP-1 RA on the prevention of stress-hyperglycemia and modulation of metabolic stress during cardiac surgery. We propose a randomized study with assignment to dulaglutide or placebo three days prior to surgery in non-DM obese patients (BG<126 mg/dL, HbA1c <6.5%, BMI \geq 25, age \geq 40 years) undergoing CABG surgery.

2.1 Primary endpoint: to determine if dulaglutide can prevent stress-hyperglycemia.

2.2 Secondary endpoints: to determine if dulaglutide can result in a lower mean BG during ICU and hospital stay. We will also explore the need of rescue therapy with insulin and differences in clinical outcomes.

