Exclusion criteria: a) Hyperglycemia (BG > 125 mg/dl or HbA1c $> 6.5\%$) or previous treatment with antidiabetic agents; b) impaired renal function (GFR < 30 ml/min) or clinically significant hepatic failure; c) subjects with gastrointestinal obstruction expected to require gastrointestinal suction; d) patients with clinically relevant pancreatic or gallbladder disease; e) treatment with oral or injectable corticosteroid; f) mental condition rendering the subject unable to understand the possible consequences of the study; g) pregnancy or breast-feeding at time of enrollment. Additional considerations are outlined in the Human Subjects section.

Aim 2.1 Prevention of hyperglycemia (primary endpoint):

The primary endpoint of this exploratory study is to compare the frequency of stress-hyperglycemia defined as any post-CABG hospital-obtained BG > 140 mg/dl between patients randomized to dulaglutide or placebo.

Aim 2.2 Secondary Endpoints: To determine the difference between groups in mean BG level in the ICU.

Additional endpoints include differences between treatment groups on: 1) the number of patients with stress-hyperglycemia requiring rescue therapy with SC insulin after discontinuation of CII; 2) need for CII treatment of hyperglycemia in the ICU; 3) mean ICU and floor BG concentration; 4) mean insulin dose during ICU (insulin infusion per hour (unit/hour) and per day); 5) duration of CII (hours); 6) days of SC insulin after discontinuation of CII; 7) amount of SC insulin in ICU and non-ICU stay; 8) hyperglycemic events (BG ≥ 200 mg/dl) in ICU and non-ICU; 9) hypoglycemic events in ICU and non-ICU (< 70 , < 54 , and < 40 mg/dl); 10) composite of mortality and complications including sternal wound infection, bacteremia, pneumonia, acute kidney injury, and acute myocardial infarction; 11) gastrointestinal adverse events (nausea, vomiting, ileus, pancreatitis); 12) ICU and hospital LOS, and ICU readmissions; 13) cerebrovascular events; 14) ICU and hospital mortality.

Methods for Aims 2.1 and 2.2:

Treatment Groups: Patients will be randomized at pre-surgery/anesthesia visit. Patients without a history of DM will receive a single injection of dulaglutide/placebo 1-3 days prior to surgery (Fig. 8).

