Inform consent and randomization: Patients will be consented during the preoperative evaluation on admission at least 24-72 hours prior to scheduled surgery. The investigators or study coordinators will review and explain the contents of the informed consent document to the eligible patient. Additional details are outlined in the Human Subjects section.

Study Sites: This pilot study will be conducted at Emory University Hospital, Emory Midtown Hospital, and Grady Memorial Hospital, Atlanta.

ICU Stay: Study patients who develop stress-hyperglycemia ($BG > 140$ mg/dl) in the ICU will be started on intravenous CII adjusted to maintain a BG target between 100-140 mg/dl following a standard hospital protocol.

Transition from ICU to Regular Floor: Patients with fasting and/or premeal $BG > 140$ mg/dl will receive coverage with sliding scale insulin (supplements), those with 2 consecutive $BG > 180$ mg/dl, or average daily $BG > 180$ mg/dl will be started on rescue therapy with SC basal insulin (glargine or levemir) once daily.¹¹¹

Rescue Therapy with Basal Insulin in Non-ICU Settings¹¹¹:

- BG between 140-200 mg/dl= start basal insulin at 0.1 units per kg weight per day.
- BG between 201-400 mg/dl= start basal insulin at 0.2 units per kg weight per day.
- Basal insulin will be given once daily, at the same time of the day.

Insulin adjustment and supplemental (correction) insulin: we will use a standard insulin treatment protocol.^{4,86}

Investigational drugs:

- Dulaglutide injection: 0.75 mg/0.5 mL solution in a single-dose pen will be provided to patients
- Saline injection/0.5 mL pre-drawn solution, a tuberculin syringe will be provided to patients
- A research pharmacist at the site-specific Clinical Research Network Unit will provide dulaglutide and saline. Patients will be instructed on self-injection technique.

Withdrawal Criteria (please see additional details in Human Subjects and DSMP sections):

- The subject may withdraw at any time during the study by primary care provider or research team.
- The subject may be withdrawn at the investigator's discretion due to a safety concern or for contravention to the inclusion and/or exclusion criteria.
- Subject diagnosed with acute pancreatitis by clinical and/or radiographic criteria.

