Analysis: The primary endpoint of Aim 2 is the frequency of stress-hyperglycemia ($BG > 140$ mg/dl) requiring insulin therapy during the postoperative period (Aim 2.1). We will use two-sided Chi-square test or Fisher's exact test for the primary outcome. In Aim 2.2 we will compare the difference in mean BG upon ICU arrival and the frequency of rescue therapy with SC insulin after transition to regular floor. We will also explore differences in complications between groups. Secondary outcomes of interest can be a binary outcome (e.g. whether CII is needed in ICU), or a count outcome (e.g. number of perioperative complications), or a continuous outcome (e.g. mean ICU BG concentration). We will adopt the same strategy proposed for the primary outcome to analyze any binary secondary outcomes. For secondary outcomes measured as counts, we plan to use nonparametric tests such as Krustal-Wallis tests. Univariate Poisson regression (or Negative Binomial regression) will be performed to estimate the marginal treatment effect. In addition, we will also conduct multivariate Poisson regression (or Negative Binomial regression) to assess the outcome differences between the two study groups with potential confounders considered. For secondary endpoints that produce continuous outcomes, we will use two-sample t-tests or nonparametric Wilcoxon tests to compare study groups.

Transformations will be applied if normality violation is detected.

Aim 2.3. To compare changes in metabolites and biomarkers in response to dulaglutide or placebo (measured in Aims 1.1 and 1.2), as well as beta-cell function and insulin resistance estimates.

Methods: Biomarkers and assessment of candidate metabolites will follow the same procedures as specified in Aim 1. Surrogates of beta cell function and insulin resistance will be derived from glucose, insulin, and c-peptide measurements acquired during the perioperative period.

[figure not shown]

Figure 8. Treatment groups in Aim 2. Patients will be assigned to receive dulaglutide or placebo 1-3 days before surgery.

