Analytic Techniques: Glucose levels will be analyzed by the hexokinase method (Beckman-Coulter, Los Angeles, CA). Insulin and C-peptide levels will be measured by two-site sequential chemiluminescent immuno-metric assays as previously described. Surrogates of beta cell function (HOMA-B) and insulin resistance (HOMA-IR) will be derived from fasting glucose, c-peptide and insulin. Only glucose and c-peptide will be measured serially after surgery (given high likelihood of exposure to exogenous insulin).

Analysis: We will integrate analyses from Aims 1 and Aims 2 to evaluate the role of dulaglutide on metabolites, metabolic pathways and biomarkers. We will use univariate and multivariate statistical methods, such as linear mixed effects models with post-hoc Tukey tests, LIMMA, and multilevel sparse Partial Least Squares Discriminant Analysis (msPLSDA), as described in Aim 1.

Expected outcomes in Aim 2: In Aim 2.1 we expect to observe a decrease in the number of patients with stress-hyperglycemia with low risk of hypoglycemia with dulaglutide therapy. We expect to find a least an 18 mg/dl (1 mmol/l) mean difference in BG between groups during ICU stay. In Aim 2.2 we don't expect to find differences in hospital outcomes. In Aim 2.3 We expect to observe differential changes in up or down regulation of metabolic pathways in response to dulaglutide compared to placebo.

Potential Pitfalls, and Possible Solutions, Alternative Consideration: Recruitment and retention of patients are important challenges in RCTs; however, Emory University and affiliated hospitals serve as cardiovascular referral center to a large population in the city of Atlanta, with over 1,000 major cardiac surgeries performed yearly. In our previous trial we recruited 340 patients over 3 years, therefore we expect to have enough time during the award period to complete enrollment (please see research timeline). It is possible that dulaglutide does not have an effect on the prevention of hyperglycemia. This information will help us understand the contribution of the incretin pathway to glucose metabolism during surgical stress.

E. Risks to Human Subjects

E.1.1 Human Subjects Involvement, Characteristics, and Design

- Description and justification for proposed involvement of human subjects:**

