- Data collection and data entry. Study members will enter baseline and daily data for this study into data collection paper forms and into an electronic database provided by the Emory Research Information Technology Department. Baseline data will include demographics/history form (subject gender, date of birth, ethnicity, dates of hospitalization and operation, history of diabetes, and comorbid conditions, body weight, BMI, smoking status, type of surgery, APACHE score. Daily information will be collected on treatment (insulin IV or SC and dosage, antibiotics, use of corticosteroids), nutrition support, BG and laboratory values, hospital complications and adverse events, and length of ICU and hospital stay.

E.1.3. Potential Risks

- **Potential Risks/Discomforts:**
 - a. Venipuncture: There is some minor discomfort and risk of mild bruising during venipuncture. Standard sterile techniques will be used during phlebotomy; thus, infection is unlikely. Disposable pre-sterilized needles and syringes will be used for all blood drawing in this study; needles and syringes will not be reused. Discomforts associated with venipuncture are rapidly reversible. Approximately 40 mL of blood will be obtained for all the blood measurements proposed.

- b. Hypoglycemia: In our previous ICU studies, we observed that <10% of cardiac surgery subjects during CII and 20-30% during SC insulin experienced hypoglycemia. No episodes of severe hypoglycemia were observed during CII in our study. The use of insulin in combination with GLP1-RA may increase the risk of hypoglycemia. The number of mild (≤ 70 mg/dL) and severe hypoglycemia (≤ 40 mg/dL) and clinical consequences (neurological and cardiovascular) will be compared between groups. Treatment of hypoglycemia: hypoglycemia, defined as a BG <70 mg/dL will be treated by a standard hypoglycemia protocol available at each hospital.
- c. Hyperglycemia: it is very likely that a high proportion of patients randomized to placebo develop hyperglycemia. All subjects with hyperglycemia (in both groups) will be treated by standard protocols in the ICU units at each hospital. We expect that ~50-60% of subjects randomized to placebo will experience one or more episodes of hyperglycemia. The frequency of severe hyperglycemia will be analyzed statistically.

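### The 25 per arm given for 80% power on mean BG fits an SD of about 20 mg/dl, not the stated 40 (power about 28%), and the Aim 2.2 analysis sentence names BG on ICU arrival where the endpoint is mean ICU BG

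*Combined protocol and SAP*

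**What the plan says.** **Endpoint.** The Aim 2.2 Secondary Endpoints text opens with "To determine the difference between groups in mean BG level in the ICU". It then lists the rest under "Additional endpoints include differences between treatment groups on", where item 3 is mean BG in the ICU and on the floor.

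**Analysis.** The Analysis paragraph that follows the withdrawal criteria says of Aim 2.2 that "we will compare the difference in mean BG upon ICU arrival", together with the frequency of SC rescue insulin. The same paragraph gives as an example of a secondary outcome "or a continuous outcome (e.g. mean ICU BG concentration"), and assigns continuous outcomes to two-sample t or Wilcoxon tests.

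**Insulin in the ICU.** Under ICU Stay, study patients who develop BG above 140 mg/dl "in the ICU will be started on intravenous CII adjusted to maintain a BG target between 100-140 mg/dl". Section E.1.3 adds: "All subjects with hyperglycemia (in both groups) will be treated by standard protocols in the ICU units at each hospital".

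**Power.** E.1.9 takes 143 versus 127 mg/dl from non-diabetic patients in the earlier CABG trial, assumes an SD for mean BG bounded at about 40 mg/dl, and states that 25 per arm give 80% power at alpha 0.05 for a 16 mg/dl difference (t or Wilcoxon test). It names no time window for this mean BG. After about 15% attrition it arrives at 60 patients, and says this total serves both of its calculations.

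**The concern.** The power statement does not follow from its own inputs, and it is one of the two supports offered for N=60. Someone using this exploratory trial to plan the next one would take from E.1.9 that 25 per arm can detect 16 mg/dl at an SD of 40, which is far from true.

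The endpoint conflict is linked to this. A BG value on ICU arrival precedes any infusion started in the ICU. An ICU mean includes values recorded after the infusion has begun in patients of either arm who exceed 140 mg/dl. The two can have different treatment differences and different SDs. Until the plan says which one answers Aim 2.2, the reader cannot tell which SD belongs in E.1.9, and a small difference in the ICU mean could be misread as a weak drug effect when it partly reflects insulin given in both arms. The documents do not allow the size of that influence to be derived.

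**Working it through.** **Inputs.** From E.1.9: difference 143 − 127 = 16 mg/dl; SD 40; alpha 0.05; 25 per arm; power 80%; attrition about 15%. From E.1.1: 30 per arm randomised. From C.2: SDs of mean ICU daily BG of 14 (intensive arm) and 20 (conservative arm); pooled √((14² + 20²)/2) = √298 = 17.3. E.1.9 does not say whether this test is one- or two-sided; I use two-sided, as the plan does for the primary outcome, and check one-sided.

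**Step 1: can 25 per arm be reproduced?** n per arm = 2·SD²·(1.960 + 0.842)²/difference², where (1.960 + 0.842)² ≈ 7.85.

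- SD 40: 2 × 1600 × 7.85/256 = 98.1, so 99 (exact t: 99.1, so 100).
- SD 20: 2 × 400 × 7.85/256 = 24.5, so 25.

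The stated figure is reproduced at SD 20 and not at SD 40. Solving the exact t calculation for the SD gives 19.8 at 25 per arm and 21.8 at 30 per arm.

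**Step 2: power at the stated inputs.** Standardised difference 16/40 = 0.40; noncentrality 0.40 × √(25/2) = 1.41. Normal approximation: Φ(1.41 − 1.96) = 0.29. Exact noncentral t: 0.283. With 30 per arm: 0.332.

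**Step 3: do other readings of the test rescue it?** All at SD 40, for 25 / 30 per arm:

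- One-sided t: 0.40 / 0.45.
- Wilcoxon, simulated on normal data: 0.27 / 0.31.
- Difference of 18 instead of 16: 0.34 / 0.40.

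None approaches 0.80.

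**Step 4: power for 16 mg/dl across SDs (two-sided t).**

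| SD (mg/dl) | Source | 25 per arm | 30 per arm | n per arm for 80% |
|---|---|---|---|---|
| 14 | C.2, intensive | 0.98 | 0.99 | 13.1 |
| 17.3 | C.2, pooled | 0.89 | 0.94 | 19.3 |
| 20 | C.2, conservative | 0.79 | 0.86 | 25.5 |
| 30 | midpoint of 20 and 40, illustration only | 0.46 | 0.53 | 56.2 |
| 40 | E.1.9 | 0.28 | 0.33 | 99.1 |

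The difference detectable with 80% power at 25 per arm is 14.0 mg/dl at SD 17.3 and 32.3 mg/dl at SD 40. The 95% CI half-width is 9.8 and 22.7 mg/dl respectively.

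**Step 5: the attrition step.** 50/0.85 = 58.8, rounded up to 60. This is sound, so the fault lies in the SD or the stated power, not in the inflation.

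**Step 6: the endpoint text side by side.** The endpoint section, the example of a continuous outcome and the Expected outcomes text all refer to BG during the ICU stay. Only the sentence that says what Aim 2.2 will compare refers to arrival.

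**The case against.** **An SD bounded at 40 may be meant as a ceiling.** That is a fair reading of the wording. But E.1.9 gives no other SD, and at the ceiling power is 28%, so the sentence cannot claim to secure 80%.

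**The only observed SDs support the sample size.** This stands, and it limits the point. A reader might infer that the trial is badly underpowered for mean ICU BG. The documents do not support that: at the C.2 SDs, power is 0.79 to 0.98 at 25 per arm and 0.86 to 0.99 at 30. Those SDs cover the whole earlier trial, diabetic patients included, so they are a guide only.

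**Mean ICU BG already has an analysis.** Correct. A reader might infer that the endpoint is left untested, but the same paragraph lists it as a continuous outcome with a t or Wilcoxon test. What remains is that the sentence specific to Aim 2.2 names a different variable.

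**Other apparent conflicts do not hold.**

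- The Specific Aims wording, "to determine if dulaglutide can result in a lower mean BG during ICU and hospital stay", is covered by the ICU endpoint plus item 3 of the additional endpoints.
- The expected "18 mg/dl (1 mmol/l) mean difference in BG between groups during ICU stay" is stated as a minimum, so powering for 16 is compatible with it.
- E.1.9 does not present 16 mg/dl as a predicted dulaglutide effect; it justifies the figure by its association with fewer complications.

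**Comparing arms under common insulin treatment is a legitimate choice.** Agreed. The need for CII, insulin dose and infusion duration are already listed endpoints. The plan only has to say which glucose variable it means.

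**Conclusion.** The point holds in two parts.

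1. The E.1.9 power statement is internally inconsistent. With 16 mg/dl, SD 40 and two-sided alpha 0.05, power is about 28% at 25 per arm and 33% at 30, and about 100 per arm would be needed for 80%. The printed 25 per arm fits an SD of about 20. The text cannot settle whether the SD is a misprint or the calculation used another value, but C.2 makes the printed SD the likelier fault. This is not a case for changing N.
2. The endpoint text and the Aim 2.2 analysis sentence name different variables: the ICU mean and the arrival value. This is a conflict over which one answers the aim, not a missing analysis.

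The figures assume roughly normal data, equal arms and independent patients. The documents give no SD for arrival BG, so no power can be stated for that variable. The trial is exploratory and this is a secondary endpoint, so the risk is misreading this result and its precision, not losing the trial. The correction should be made before analysis.

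**What to change.** N stays at 60, and no change to insulin management is proposed.

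1. **E.1.9.** Name mean ICU BG as the powered variable. Then either replace SD 40 with a justified value, such as those in C.2, or keep SD 40 and restate the power as about 28% at 25 per arm (33% at 30). In both cases show power over SD 14 to 40. Possible wording: for mean ICU BG, a 16 mg/dl difference with 25 evaluable patients per arm has two-sided power of 98%, 89%, 79% and 28% at SDs of 14, 17.3, 20 and 40 mg/dl.
2. **Analysis paragraph, Aim 2.2 sentence.** Change the variable to mean ICU BG, to match the endpoint section, and say how each patient's ICU mean is formed. Keep BG on ICU arrival as a supportive comparison.

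**Cost.** Two wording edits and a restated power paragraph. The stated power may become less favourable. Aim 1 already classifies patients by BG on ICU arrival, and placebo patients feed into that cohort; the team should confirm that the arrival reading can be identified in the dulaglutide arm as well. Arrival BG may also reflect insulin given during surgery, on which the documents are silent; this is a further reason to keep it supportive.

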C.2. GLUCO-CABG Trial:²⁴ in this RCT we aimed to determine whether intensive BG control (target: 100-140 mg/dl) could reduce perioperative complications compared to conservative BG control (141-180 mg/dl) in hyperglycemic patients undergoing CABG. A total of 302 patients were randomized to intensive (n=151) or conservative (n=151) glucose control. The mean ICU daily BG was 132 ± 14 mg/dl (IQR 124-139) in the intensive and 154 ± 20 mg/dl (IQR 142-164) in the conservative group ($p < 0.001$). Overall, we observed a similar number of patients in the intensive and conservative groups experiencing ≥ 1 complications (42% vs. 52%, $p = 0.08$). We observed no differences in the composite or individual complications in patients with DM; however, the composite of complications was lower in non-DM patients with stress-hyperglycemia assigned to the intensive group, $p = 0.008$, (Fig.2). Since all patients enrolled GLUCO-CABG patients had stress-hyperglycemia, we recently *analyzed phenotypic and biological characteristics of non-diabetic individuals at risk for perioperative stress hyperglycemia during CABG*. The two most important features in patients who developed >2 episodes of BG >140 mg/dL were older age (67.0 ± 9.2 vs 59.1 ± 9.4 , $p = 0.004$) and higher BMI (28.9 ± 5.8 vs 26.1 ± 4.3 , $p = 0.06$). All six patients older than 50 years and BMI >30 kg/m² developed hyperglycemia. These characteristics were confirmed in an additional cohort (i.e. age >45 years). Older age and obesity are well-established risk factors for insulin resistance and DM.

C.3. Inflammatory markers during CABG: Circulating levels of cortisol, inflammatory and oxidative stress markers increase for several days in the perioperative period (Fig. 3). No difference was observed between conservative and intensive insulin therapy groups in the perioperative period of patients undergoing CABG surgery. Changes in these markers did not explain the benefits associated with tighter glycemic control with insulin therapy.³

C.4. GLP-1 RA safety and non-inferiority to insulin therapy.

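### ICU insulin dose and CII duration (additional endpoints 4 and 5) have no rule for patients who never receive CII, so the test can fall on a subset selected by treatment effect

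*Combined protocol and SAP*

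**What the plan says.** Section D2, Aim 2.2, introduces its list with "Additional endpoints include differences between treatment groups on". Items 4 and 5 are "mean insulin dose during ICU (insulin infusion per hour (unit/hour) and per day); 5) duration of CII (hours". Item 2 of the same list is a separate yes/no endpoint: "2) need for CII treatment of hyperglycemia in the ICU".

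The ICU Stay paragraph sets who gets an infusion: "Study patients who develop stress-hyperglycemia ($BG > 140$ mg/dl) in the ICU will be started on intravenous CII".

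The Analysis paragraph for Aims 2.1 and 2.2 says of continuous secondary endpoints: "we will use two-sample t-tests or nonparametric Wilcoxon tests to compare study groups". For yes/no outcomes it gives need for CII as its example: "Secondary outcomes of interest can be a binary outcome (e.g. whether CII is needed in ICU".

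Section E.1.3, under hyperglycemia, gives the expected frequency: "We expect that ~50-60% of subjects randomized to placebo will experience one or more episodes of hyperglycemia".

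The documents do not say whether a patient without CII enters endpoints 4 and 5 as zero or is left out, whether units per hour means per infusion hour or per ICU hour, or which patients form the analysis population.

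**The concern.** An infusion is started by a glucose reading after randomization, and that reading is almost the same as the primary outcome. If endpoint 4 is computed per hour of infusion, a patient without an infusion has no value and drops out of the test. The same happens to endpoint 5 if the duration field is left blank. The test then compares placebo patients who became hyperglycemic with dulaglutide patients who became hyperglycemic despite treatment. Randomization does not make those two subsets comparable.

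If dulaglutide keeps some patients off insulin, the patients who would show the saving are the ones removed. The users-only comparison can then understate the reduction in insulin. If the patients kept off insulin are mainly the milder cases, it can point the wrong way. Aim 2 exists to give preliminary estimates for planning later trials, so a distorted estimate of insulin amount could be carried forward.

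**Working it through.** The plan states no effect, power or sample size for endpoints 4 and 5, so there is no figure of its own to reproduce.

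**1. How many patients are affected.** Allocation is 30:30 (E.1.1). Assume every patient with hyperglycemia gets CII; the D2 Rationale says most do.
- At 50-60% (E.1.3): 30 × 0.50 = 15 to 30 × 0.60 = 18 placebo patients with CII, so 12 to 15 without.
- At 60-80% (Specific Aims): 18 to 24 with CII, so 6 to 12 without.

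**2. Infusion rate under a uniform shift.** Assumptions not in the documents: ICU glucose without insulin is normal with placebo mean m = 140-150 mg/dl; the rate is 1 U/h at 140 mg/dl plus 0.05 U/h per mg/dl above, and 0 at or below 140. The SD s runs from 20 to 40; section E.1.9 uses about 40 for mean glucose. The shift is 16 mg/dl, the difference used in E.1.9.

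With d = (m − 140)/s:
- share on CII: P = Φ(d)
- mean excess over 140: E = s[φ(d) + dΦ(d)]
- all-patient mean rate: P + 0.05E
- users-only mean rate: (P + 0.05E)/P

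Example with m = 145, s = 25:
- Placebo: d = 0.20, P = 0.579, E = 12.67. All-patient rate 0.579 + 0.634 = 1.213 U/h; users-only 1.213/0.579 = 2.09 U/h.
- Dulaglutide: mean 129, d = −0.44, P = 0.330, E = 5.42. All-patient rate 0.330 + 0.271 = 0.601 U/h; users-only 0.601/0.330 = 1.82 U/h.
- Fall: 50% over all patients, 13% in users.

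| Placebo mean, SD | On CII, placebo v dulaglutide | Fall, all patients | Fall, users only |
|---|---|---|---|
| 140, 20 | 50% v 21% | 63.1% | 12.8% |
| 140, 40 | 50% v 34% | 37.9% | 9.9% |
| 145, 25 | 58% v 33% | 50.4% | 13.0% |
| 150, 20 | 69% v 38% | 53.3% | 15.5% |
| 150, 40 | 60% v 44% | 34.4% | 10.8% |

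The users-only figure keeps the right sign but shows about 10-15% where the all-patient figure shows 34-63%.

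**3. When the sign reverses.** Same dose function, placebo mean 148, SD 25 (63% on CII; 1.35 U/h over all patients, 2.16 U/h in users). Only patients below a cut-off respond.

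| Responders below | Drop (mg/dl) | All-patient change | Users-only change |
|---|---|---|---|
| 165 | 25 | −45% (to 0.74 U/h) | +39% (to 2.99 U/h) |
| 180 | 25 | −59% | +4% (to 2.25 U/h) |
| 200 | 25 | −66% | −15% (to 1.84 U/h) |
| 165 | 16 | −34% | +11% |
| 180 | 16 | −42% | −4% |

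The large reversal depends on 165 − 25 = 140: every responder lands on or below the CII threshold, and no remaining user benefits.

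**4. CII duration, a separate simulation.** Assumed: 60% of placebo and 30% of dulaglutide patients on CII; placebo users' duration lognormal with mean 24 h and coefficient of variation 0.8.

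| Who is kept off CII | Users only (h) | All patients, zeros included (h) |
|---|---|---|
| Unrelated to severity | 24.0 v 24.0 | 14.4 v 7.2 |
| Mildest cases | 24.0 v 36.4 | 14.4 v 10.9 |
| Mildest cases, rest 25% shorter | 24.0 v 27.3 | 14.4 v 8.2 |
| Uniform shortening | 24.0 v 17.7 | 14.4 v 5.3 |

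With zeros included, dulaglutide has the lower mean in every case. Among users the effect is hidden, reversed or kept, depending on the mechanism.

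**The case against.** The strongest reply is that the plan never restricts the analysis to CII users. It speaks of treatment groups and study groups. A patient with no infusion has 0 hours of CII and 0 units per day, and the reference to the ICU in endpoint 4 could make ICU time the denominator, which would define the rate for everyone. This stands. A reader might infer that the plan specifies a users-only comparison, or that neither endpoint has a value without CII. The text supports neither. What remains is that the units-per-hour measure is worded as an infusion rate, its denominator is not fixed, and nothing prevents non-users from being dropped.

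Second, need for CII is endpoint 2 and is compared by chi-square or Fisher's exact test. An effect through avoided infusions would show there. This also stands, although that endpoint cannot say how much insulin was spared.

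Third, reversal needs a response sharply tied to severity, which nothing in the documents suggests. A reader might infer from the +39% case that reversal is likely. It is one edge of the assumptions, and it shrinks or disappears as the cut-off rises.

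Fourth, section C.2 notes of the team's earlier trial: "Since all patients enrolled GLUCO-CABG patients had stress-hyperglycemia". That explains why the question may not have arisen there. It is not evidence of how non-users will be handled here.

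Finally, these are two of 14 additional endpoints in a 60-patient exploratory study. That limits the stakes, but the remedy is nearly free.

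**Conclusion.** The concern holds as a missing rule with a foreseeable consequence. Endpoints 4 and 5 lack a value, a denominator and a population for patients who never receive CII. On the plan's own 50-60% figure these are 12 to 15 of 30 placebo patients, if all with hyperglycemia get CII. A test limited to users would not be protected by randomization and would probably understate insulin sparing. Reversal is possible but needs response strongly concentrated in milder cases.

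The sizes rest on an assumed glucose distribution, dose function and duration distribution. They illustrate direction and order of magnitude and do not predict the trial's result. The primary endpoint, mean ICU glucose and need for CII are unaffected. Only the exploratory estimate of insulin amount is concerned.

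**What to change.** Add a sentence to each endpoint in Aim 2.2 and to the Analysis paragraph:
- Analyze endpoints 4 and 5 in all randomized patients who had surgery, with 0 units and 0 hours for those who never received CII.
- Define the dose as total ICU intravenous insulin units per ICU day for each patient.
- Compare the groups by Wilcoxon test.
- State how deaths and very short ICU stays are handled, since zero or low use can arise for those reasons too.
- Report infusion rate and duration among CII users as description only, without a test.

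Insulin dosage and length of ICU stay are already collected (section E.1.2), so no new data are needed. The small downside is many tied zeros, which the Wilcoxon test accommodates.
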